5.1 Primary Objectives

The Aim 1 objective from the CAPTURE protocol is to define the sensitivity and specificity of CAPTURE for identifying previously undiagnosed patients with clinically significant COPD in a broad range of primary care settings. The Aim 2 objective of the CAPTURE protocol is to explore clinical practice implementation approaches to and acceptance of CAPTURE case finding for clinically significant COPD in a range of primary care practices. The objective of the cluster-randomized trial described in Aim 3 of the CAPTURE protocol is to define the impact of CAPTURE information provided to clinicians in identifying and managing CAPTURE+ patients across a broad range of primary care settings. Table 1 below outlines primary and secondary objectives and endpoints for the cluster-randomized trial described in Aim 3 of the CAPTURE protocol.

Table 1. CAPTURE Study Objectives, Endpoints for Aim 3.

| OBJECTIVES | ENDPOINTS |
|---|---|
| Primary | |
| Define the impact of CAPTURE information provided to clinicians in identifying and managing CAPTURE+ patients across a broad range of primary care settings. | Proportion of CAPTURE+ participants who meet at least one of the following within 12 months of study baseline (composite endpoint): 1) referral for or completion of clinical spirometry testing, 2) new diagnosis of COPD, 3) newly prescribed respiratory medication (long acting bronchodilator or anti-inflammatory for respiratory condition), 4) referral to a specialist for respiratory evaluation/treatment, or 5) referral for or completion of pulmonary rehabilitation. |
| Secondary | |
| Define the impact of providing CAPTURE education and patient-level CAPTURE information to clinicians on selected clinician interventions for the management of CAPTURE+ patients. | Proportion of CAPTURE+ participants who have each of the following occur within 12 months of study baseline (separate endpoints to be evaluated individually): 1-5) each component of the Aim 3 primary endpoint, and 6) recommendation or administration of influenza vaccination. |

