Height and Weight: Height and weight will be recorded in order to determine appropriate prediction equations for spirometry and possible effect of obesity on spirometry. Height will be recorded in inches, and weight will be measured in pounds.

Demographic Data Collection: Demographic data including date of birth, gender, ethnicity, race, educational level, current employment status, living arrangement and health insurance will be entered into the EDC system.

Medical History: Previous medical diagnoses will include comorbidities such as cardiovascular, respiratory, and malignant disorders. Influenza vaccination history will also be recorded.

Statistical Analysis Plan

CAPTURE

Concomitant Medication Review: Respiratory medications will be recorded at baseline for all participants.

CAPTURE Additional Items Questionnaire: Participants will complete the 13 item self-administered questionnaire.

COPD Assessment Test (CAT): Participants will complete the eight item self-administered questionnaire. Each item is on a scale of 0-5 with higher scores indicating worse health status.

Respiratory Symptoms, Smoke Exposure and Exacerbation-Like Events: History of respiratory symptoms and exacerbation like events over the past year as well as smoke exposure (including e-cigarette or equivalent) will be recorded.

Adverse Events: Adverse events related to study procedures will be recorded by the coordinator.

Practice Characteristics: The locations of participating clinical practices will be categorized based on designation as rural by the Federal Office of Rural Health Policy (FORHP) / Health Resources & Services Administration (HRSA). A practice location will be classified as rural if the ZIP code appears in the Eligible ZIP Codes file downloadable from the FORHP website: <https://www.hrsa.gov/rural-health/about-us/definition/datafiles.html>. Other data describing the characteristics of participating practices will be collected from study site personnel.

6.6.2: Longitudinal follow-up

Follow-up efficacy assessments are collected from the time of baseline to 12 months in selected cohorts (as described in section 6.1).

Table 3: Data collected from medical records include:

| All participants undergoing 12-month follow-up as described in section 6.1 | Current Smokers Only |
|--|--|
| Clinical spirometry ordered or administered | Smoking cessation counseling |
| New recorded clinical diagnosis of COPD | New prescription for smoking cessation medication |

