
9.5 Missing Data

Baseline data, except for spirometry measurements, are expected to have few or no missing values. Baseline spirometry measurements are expected to be missing for a small portion of patients due to patient refusal/inability, administration error, or spirometry measurements having insufficient quality. Data from the 12-month medical record review are expected to be missing for a small portion of patients (among those selected for follow-up) due to various problems accessing the medical record. Data from the 12-month patient survey are expected to be missing for a significant portion of patients due to patients not returning completed surveys.

Any missing data or data anomalies will be communicated to the site(s) for clarification/resolution. We will summarize the extent of missing data by intervention group. Patient demographics, other baseline characteristics, and available 12-month follow-up data will be compared between those with and without complete follow-up data, among those who were prospectively selected for follow-up, overall and by intervention group.

The primary analysis of the primary and secondary endpoints will be among those with complete follow-up (complete data for the relevant portions of both the chart review and follow-up survey).

For each Aim 3 endpoint that is collected via both medical record review and patient survey, sensitivity analyses will be conducted by imputing missing outcome data using different assumptions and applying the primary analysis method to the resulting data sets. Sensitivity analyses will include

1. Imputation of negative responses (i.e., responses indicating that the outcome has not occurred) for all missing patient survey responses, followed by analysis of all patients with medical record review data
2. Imputation of positive responses (i.e., responses indicating that the outcome has occurred) for all missing patient survey responses, followed by analysis of all patients with medical record review data; and
3. Multiple imputation of all missing outcome data using the observed outcomes and covariates, as described below, followed by analysis of all patients selected for follow-up.

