Additional baseline predictors for imputing outcome variables will be included in the imputation procedure based on examination of study data that are blinded with respect to intervention group (pooled across intervention groups), assessing the association of each baseline variable with 1) whether the outcome data is missing, and 2) the outcome itself (among those with complete outcome data). To avoid including extraneous predictors, which may cause problems in fitting the logistic regression models and generating accurate imputations, we will use only baseline predictors that are associated with *both* the outcome missingness *and* the outcome itself, for at least one outcome in the group, based on p-values <0.01 from t tests¹ and chi-square tests². These additional baseline predictors will be selected separately for the medical record review variables and for the follow-up survey variables.

Based on the study data on March 21, 2023, from study sites for which all follow-up data have been collected (representing about 84% of the patients selected for follow-up), the additional baseline predictors for each outcome group would be the following:

| Outcome variable(s) | Predictors for medical record review | Predictors for follow-up survey |
|---------------------------------|--|---|
| Pulmonary care outcomes | PBRN Practice type Practice size (# clinicians) Patient enrollment date Education | Race Education Health insurance Smoking status FEV ₁ % predicted |
| Flu vaccination | PBRN Practice type Practice is a residency site Race Ethnicity Education | PBRN Age Race Education Health insurance Ever had flu shot |
| Smoker-specific outcomes | PBRN Practice type Practice is a residency site Practice size (# clinicians) Education | PBRN |

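### Baseline influenza vaccination history is collected and passed the SAP's own blinded screen for the survey flu outcome, but no specified efficacy model for the influenza vaccination endpoint adjusts for it

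*SAP*

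**What the plan says.** - **Endpoint.** SAP 5.1, Table 1 lists, after the five components of the composite, "6) recommendation or administration of influenza vaccination" as a separate secondary endpoint.
- **Baseline variable.** SAP 7.6 (Medical History): "Influenza vaccination history will also be recorded". SAP 9.5 expects few or no missing baseline values apart from spirometry.
- **Screen.** SAP 9.5 picks extra imputation predictors from data pooled across arms. A variable must be "associated with *both* the outcome missingness *and* the outcome itself, for at least one outcome in the group", at p<0.01. For the flu survey variable the resulting list is "PBRN Age Race Education Health insurance Ever had flu shot". The medical-record list for flu vaccination does not contain flu-shot history.
- **Main analysis.** SAP 9.5 uses patients with complete chart and survey data. SAP 11.1 fits an identity-link, exchangeable GEE on arm alone.
- **Sensitivity analyses.** For endpoints collected from both sources, "sensitivity analyses will be conducted by imputing missing outcome data using different assumptions and applying the primary analysis method to the resulting data sets". These are all-negative, all-positive and multiple imputation.
- **Adjusted models.** SAP 11.2 describes multivariable GEE models for the composite and for its components. Influenza vaccination is neither and is not named in 11.2. Vaccination history is not among the covariates in 9.4 or the baseline variables in 10.3.

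**The concern.** The investigators have collected a baseline variable closely related to this outcome, and their own blinded data link it to the survey-reported outcome and to whether the survey is returned. The planned effect estimates still ignore it. Two things could be lost.

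1. **Precision.** A baseline variable that explains outcome variance narrows the interval for the arm difference, and this one is already in the database.
2. **Protection against selective response.** Surveys are expected to be missing for many patients; SAP Table 9 shows 248 of 380 complete (65%) in March 2020. If flu-shot history shapes response differently in the two arms, a complete-case comparison on arm alone carries that difference into the estimate.

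Practices are also randomised at activation and recruit patients afterwards, so any difference between arms in patients' vaccination habits enters the unadjusted comparison.

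**Working it through.** **1. The plan's own power figures.** SAP Table 5 (Protocol Table 9-2) concerns the composite; no figure is given for influenza vaccination. With 44 practices per arm, 5 CAPTURE+ patients each and a 5% control rate, effective n per arm = 44×5/(1 + 4×ICC). At +10 points:

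| ICC | Effective n | Recomputed | Stated |
|---|---|---|---|
| 0.05 | 220/1.2 = 183.3 | 0.894 | 0.89 |
| 0.10 | 220/1.4 = 157.1 | 0.843 | 0.84 |
| 0.15 | 220/1.6 = 137.5 | 0.793 | 0.79 |

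The table reproduces, so the same clustering formula is used in step 4. It says nothing for or against this point.

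**2. What the screen guarantees.** For a binary predictor and outcome, p<0.01 requires R² of at least 6.635/N. With N assumed, that is 0.013 at N = 500 and 0.003 at N = 2,000. The standard error ratio is √(1−R²), so the guaranteed reduction is 0.67% and 0.17%. Passing the screen does not show a strong covariate.

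**3. Plausible precision gain (assumed inputs).** Let q be the share ever vaccinated, p the outcome rate and g the outcome gap between ever and never vaccinated. Then R² = q(1−q)g²/[p(1−p)].

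- q = 0.7, p = 0.6, g = 0.2: R² = 0.21×0.04/0.24 = 0.035; SE ratio 0.982.
- q = 0.7, p = 0.6, g = 0.4: R² = 0.21×0.16/0.24 = 0.14; SE ratio 0.927.
- Over q = 0.6-0.8, p = 0.5-0.7 and g = 0.1-0.5: R² runs from 0.006 to 0.29 and the SE falls by 0.3% to about 15%. The fall is about 2% at g = 0.2 and 5-10% at g = 0.4.

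This is an upper bound, because it lets the covariate explain between-practice variance as fully as within-practice variance.

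**4. Power when only within-practice variance is explained.** Assume 44 practices per arm, 10 CAPTURE+ per practice (SAP 13.1) × 65% = 6.5 complete cases, and 60% versus 70%. Effective n = 44×6.5/[(1−ICC)(1−R²) + 6.5×ICC].

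| ICC | R² = 0 | R² = 0.10 | R² = 0.30 |
|---|---|---|---|
| 0.05 | 286/1.275 = 224.3; 0.60 | 286/1.180 = 242.4; 0.64 | 286/0.990 = 288.9; 0.71 |
| 0.15 | 286/1.825 = 156.7; 0.46 | 286/1.740 = 164.4; 0.48 | 286/1.570 = 182.2; 0.52 |

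**5. Complete-case bias with no true effect.** Bias = g × (share ever vaccinated among responders in one arm − the same share in the other). Assume 70% ever vaccinated and about 65% response in each arm. Response is given as ever / never vaccinated.

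- Same pattern in both arms (70% / 53.3%): shares equal, bias 0.
- Mildly different (72% / 48.7% versus 68% / 58%): shares 0.504/0.650 = 0.775 and 0.476/0.650 = 0.732. Bias is 0.9 points at g = 0.2 and 1.7 at g = 0.4.
- Strongly different (75% / 41.7% versus 65% / 65%): shares 0.525/0.650 = 0.808 and 0.700. Bias is 2.2 and 4.3 points.

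If there is an effect and it varies with history, responders also give a different average. Take an effect of 5 points in ever and 15 in never vaccinated patients, with the same response pattern in both arms. The full-population effect is 0.7×5 + 0.3×15 = 8.0 points. Responders are 0.49/0.65 = 75.4% ever vaccinated and give 7.5.

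**6. Where the variable is used.**

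| Analysis | Uses flu-shot history? |
|---|---|
| Complete-case GEE | No |
| All-negative and all-positive imputation | No |
| Multiple imputation | Yes, in the imputation model; the fitted model is still arm-only |

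**The case against.** The case for leaving the plan alone is substantial.

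- **Multiple imputation already addresses non-response.** A reader might infer that a known predictor of non-response goes wholly unadjusted. It does not. Influenza vaccination has its own imputation group, its survey model contains flu-shot history together with arm by CAPTURE status, and SAP 11.2 repeats the secondary efficacy analyses on the imputed data. Imputation also uses the five other variables in the same list, which a single added covariate would not. This stands; the gap is confined to the complete-case and single-imputation analyses.
- **The association is shown only for the survey variable.** History did not qualify for the chart variable. The list is provisional (March 2023, about 84% of patients selected for follow-up) and is not restricted to CAPTURE+ patients. The screened item, "Ever had flu shot", is a lifetime history, whereas the outcome is "recommendation or administration of influenza vaccination" within 12 months and so partly clinician behaviour. This stands.
- **The survey source itself is unclear.** SAP Table 4 and Protocol 8.2 list no vaccination item in the patient survey, although SAP 9.5 treats flu vaccination as a survey outcome. If the endpoint comes from the chart alone, the survey non-response argument falls away.
- **Large gains need strong assumptions.** It is tempting to say that adjustment would lift 80% power to 90%. That needs a correlation of 0.5 acting between and within practices alike. At 70% ever vaccinated and a 60% outcome rate, this means a gap of 0.5×√(0.24/0.21), about 53 points. No document supports that.
- **The arm-only test is valid.** Chance imbalance is covered by the clustered standard error, and no recruitment imbalance is documented. Protocol 9.1.2.2 calls these secondary analyses exploratory, and SAP 9.7 asks for caution with their p-values.

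What survives is narrower: a cheap, already collected covariate is missing from every specified effect model for this endpoint, and imputing with it does not give the precision of adjusting for it.

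**Conclusion.** The point holds as a minor, optional improvement. No specified efficacy model for the influenza vaccination endpoint contains baseline vaccination history, although the SAP's provisional screen ties that history to the survey outcome and its missingness.

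The cost is mainly precision. The screen alone guarantees under 1% off the standard error. The range of 0.3% to 15% rests on assumed vaccination rates, outcome rates and outcome gaps, none of which the documents give.

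A reader might infer that the complete-case result is biased. The documents do not show this. With no true effect, bias needs response by vaccination history to differ between arms, and then runs from 0.9 to 4.3 points in the scenarios worked here. If the effect varies with history, responders estimate a somewhat different average. Nothing here touches the primary composite endpoint.

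**What to change.** 1. In SAP 11.2, name the influenza vaccination analysis. Specify the practice-clustered GEE with arm and baseline influenza vaccination history as covariates, state the link, and report a risk difference standardised over the baseline distribution of the CAPTURE+ population.
2. Limit the adjusted model to CAPTURE+ patients, so that it need not be run across all eight populations and every 9.4 subgroup.
3. Keep the arm-only and multiple-imputation results as supporting analyses.
4. Add vaccination history to the SAP 10.3 baseline table.
5. Reconcile SAP Table 4 and Protocol 8.2 (no vaccination survey item) with SAP 9.5 (flu vaccination as a survey outcome), and state the source or sources for this endpoint. This decides who counts as a complete case.

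The cost is a few sentences, one table row and one covariate; no new data are needed. The small downside is a standardised estimate in place of a single model coefficient. The change should be recorded before unblinding, as SAP 9.2 requires of decisions arising from the blinded data review.

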(<https://www.abdn.ac.uk/hsru/research/research-tools/study-design/>). These calculations assume a type I error of 5% and that the control arm meets the composite endpoint in 5% of CAPTURE+ patients, and the CAPTURE arm meets the composite endpoint in higher percentages (columns of Table 5). There will be variability in the actual number of CAPTURE+ patients per practice. It is standard practice to inflate the number of needed clusters by 12% to account for this extra source of variability. Therefore, our power calculations are based on 44 clusters per intervention arm.

9 General Analysis Considerations

| | | | | | |
|---|-------|------|------|-------|-------|
| Overall power to detect a difference in rate of meeting primary endpoint in CAPTURE group (50 practices/cluster) vs usual care (50 practices/cluster), assuming 5% performance rate in usual care; 50 patients total / practice; assuming 10% prevalence gives 5 CAPTURE+/practice. | | | | | |
| Improvement over usual care | +7.5% | +10% | +15% | +25% | +50% |
| ICC=0.05 | 0.72 | 0.89 | 0.99 | >0.99 | >0.99 |
| ICC=0.10 | 0.65 | 0.84 | 0.98 | >0.99 | >0.99 |
| ICC=0.15 | 0.59 | 0.79 | 0.97 | >0.99 | >0.99 |

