11.1 Primary Efficacy Analysis

The primary efficacy analysis is restricted to CAPTURE+ participants, denoted in section 9.3 as population 1 (Primary Analysis Population). The primary analysis will be to compare the average cluster sample proportion (average proportion of CAPTURE+ patients per practice meeting composite endpoint) between intervention arms. Practices that do not identify any CAPTURE+ subjects will not contribute to this analysis. A two-sample test comparing average cluster sample proportions will be used that explicitly takes into account correlation between individuals treated within the same practice. A two-sided p-value < 0.05 will be considered statistically significant. This analysis corresponds to a generalized estimating equation (GEE)⁴ regression analysis with (1) individual-level binary composite outcome data, (2) CAPTURE intervention group as a covariate, (3) practice id used to identify correlated outcomes, (4) exchangeable correlation matrix that assumes similar correlation between all composite outcome results for patients within the same practice, and (5) an identity link function so that the coefficient parameter corresponding to CAPTURE intervention group represents a difference in outcome probability. The primary analysis would then correspond to a test for whether the CAPTURE intervention group parameter is non-zero.

Technical Details of the Primary Analysis:

This analysis is restricted to CAPTURE+ participants (Primary Analysis Population)

Let $\pi_{ij} = P(\text{Participant } j \text{ from Practice } i \text{ Meets the Primary Endpoint})$.

Let $CAPTURE_i = I(\text{Practice } i \text{ Received Basic COPD plus CAPTURE education intervention})$

Let PRACTICE take on values $i = 1, \dots, 100$ denoting the enrolled practices

For the primary analysis, the GEE model takes the form

$\pi_{ij} = \beta_0 + \beta_1 CAPTURE_i$, where binary outcomes from the same practice are assumed to follow a compound symmetry correlation structure.

R code for the Primary Analysis:

If the R dataset representing CAPTURE+ patients is called **final** and variables are

MetComp=1 if individual met primary (composite) outcome, 0 otherwise

CAPTURE=1 if individual was from a practice randomized to the Basic COPD plus CAPTURE education intervention, 0 otherwise

Practice is a variable with values $1, \dots, 100$ denoting the enrolled practices

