Change in CAT score and change in number of episodes of respiratory illness requiring antibiotic/steroid treatment will be analyzed using mixed⁵ models with a random effect for practice. The average cluster sample proportion of patients who experience exacerbations will be compared between intervention groups using methodology similar to that used for the primary endpoint. Subject to having sufficient mortality events, survival analysis⁶ allowing for correlation of endpoints within cluster (practice) will be used to compare mortality between intervention groups and perform multivariable analysis. We will explore differences between intervention groups in the average cluster sample rate of hospitalizations again using GEE.

Secondary Analyses Using Single Imputation: Primary and secondary efficacy analyses of outcomes collected via both medical record review and patient survey will be repeated among patients with complete medical record review data, imputing a single value for missing outcome components from the patient survey. One analysis will impute a negative outcome (i.e., the event did not occur) for each missing survey response; another analysis will impute a positive outcome (i.e., the event did occur) for each missing survey response. Complete-data analyses described in sections 11.1 and 11.2 will be performed on each complete data set produced by imputation.

Secondary Analyses Using Multiple Imputation: Primary and secondary efficacy analyses will be repeated using data sets generated by the multiple imputation procedure described in section 9.5. Complete-data analyses described in sections 11.1 and 11.2 will be performed on each complete data set produced by multiple imputation. Parameter estimates and standard errors will be

combined across the multiply imputed data sets using the method of Rubin⁸, which is implemented by the `pool()` function in the R package ‘mice’. Specifically, for each parameter of interest, let Q_i be the parameter estimate from data set i , with associated complete-data variance U_i . Let m be the number of imputed data sets. Then

$$\bar{Q} = \frac{1}{m} \sum_{i=1}^m Q_i \text{ (the average of the } m \text{ estimates)}$$

is the overall parameter estimate. Let

$$\bar{U} = \frac{1}{m} \sum_{i=1}^m U_i \text{ (the average of the } m \text{ variances)}$$

and

$$B = \frac{1}{m-1} \sum_{i=1}^m (Q_i - \bar{Q})^2 \text{ (the variance in estimates between data sets).}$$

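### Every missing survey gets the same imputed value in both arms, so no planned analysis tests outcomes of non-responders that differ by arm beyond missing at random

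*SAP*

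**What the plan says.** SAP 9.5 restricts the primary analysis to patients with complete chart and survey data for the endpoint, and expects a substantial share of surveys to be missing. For endpoints drawn from both sources it lists three sensitivity analyses:

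1. All missing survey answers set to negative, among patients with chart data. SAP 11.2 repeats this: "One analysis will impute a negative outcome (i.e., the event did not occur) for each missing survey response".
2. "Imputation of positive responses (i.e., responses indicating that the outcome has occurred) for all missing patient survey responses", also among patients with chart data.
3. Multiple imputation over everyone selected for follow-up. The model includes intervention group interacting with CAPTURE status, and it uses chart data to impute survey data.

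Protocol 9.3.2 gives the same three. SAP 9.5 also tabulates missingness by arm, and compares patients with and without complete follow-up overall and by arm.

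The effect measure is a risk difference from an identity-link GEE (SAP 11.1), judged by this rule: "A two-sided p-value < 0.05 will be considered statistically significant". Neither document plans a delta-adjusted or tipping-point analysis, or any analysis in which the two arms receive different imputed values.

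**The concern.** A pair of all-negative and all-positive imputations is easily read as a worst case and a best case. For a single proportion it is. For a difference between arms it is not, because the damaging case is the one in which non-responders' unseen outcomes run in opposite directions in the two arms.

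This matters here for three reasons. The primary analysis discards survey non-responders. The only completion count in the documents, SAP Table 9, is 248 of 380. And the chart cannot fully stand in for the survey: specialist referral is a component of the composite, but it appears only in the survey list (SAP Table 4; Protocol 8.2) and not in the chart list (SAP Table 3). A reader shown three concordant sensitivity analyses could conclude that the result is robust to non-response, when the departure that threatens it was not examined.

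**Working it through.** **Inputs**

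- Control rate, SAP Section 8: "the control arm meets the composite endpoint in 5% of CAPTURE+ patients". Responders' difference: +10 points, one of the SAP Table 5 columns, so 15% versus 5%.
- Survey non-response: (380 - 248)/380 = 34.7% (SAP Table 9, 25 March 2020). It is pooled over arms and not restricted to CAPTURE+, and some surveys may still have been open.
- Non-response by arm, and the share of events that the chart captures, are not in the documents. Both are assumed and shown as ranges.

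**The plan's own figures.** SAP Section 8 states that "our power calculations are based on 44 clusters per intervention arm", with 5 CAPTURE+ patients each. The effective n per arm is 44 × 5/(1 + 4 × ICC), which is 183.3 at ICC 0.05. Two-sided power at +7.5, +10 and +15 points is then 0.721, 0.894 and 0.993, against 0.72, 0.89 and 0.99 in Table 5. The inputs are read correctly; the power table does not itself bear on this point.

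**Formulas.** Let m be survey non-response, p the composite rate in responders and c the chart-only composite rate in non-responders, with T for CAPTURE and C for control.

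- Complete case: RD = pT - pC
- All-negative: RD_neg = [(1 - mT)pT + mT·cT] - [(1 - mC)pC + mC·cC]
- All-positive: RD_pos = [(1 - mT)pT + mT] - [(1 - mC)pC + mC]

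The chart drops out of RD_pos, because one positive survey answer meets the composite.

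**All-positive rule**

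| Responders, CAPTURE / control | Non-response, CAPTURE / control | RD_pos |
|---|---|---|
| 15% / 5% | 34.7% / 34.7% | 0.653 × 10.0 = 6.5 points |
| 15% / 5% | 40% / 30% | (9.0 + 40) - (3.5 + 30) = +15.5 |
| 15% / 5% | 30% / 40% | (10.5 + 30) - (3.0 + 40) = -2.5 |
| 5% / 5% | 40% / 30% | (3.0 + 40) - (3.5 + 30) = +9.5 |

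At equal non-response the rule multiplies the responders' difference by (1 - m). At unequal non-response the term mT - mC dominates. RD_pos exceeds the complete-case difference once mT/mC is above (1 - pC)/(1 - pT) = 0.95/0.85 = 1.118. From 34.7% in control, that is a gap of about 4.1 points.

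**All-negative rule.** Suppose non-response is equal at 34.7% and non-responders have the responders' true event rates. With no chart capture, RD_neg = 0.653 × 10.0 = 6.5. With full capture it is 6.5 + 0.347 × 10.0 = 10.0. It can also exceed 10: chart-only rates of 20% versus 5% in non-responders give 6.5 + 0.347 × 15 = 11.7.

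**Arm-opposed extremes, equal non-response**

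- 34.7% missing, chart captures half of events, CAPTURE negative and control positive: (9.8 + 0.347 × 7.5) - (3.3 + 34.7) = -25.6.
- The reverse: (9.8 + 34.7) - (3.3 + 0.347 × 2.5) = +40.4.
- 35% missing and no chart capture: -28.5 and +41.5.

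**What a tipping point would show.** Take 44 practices per arm of 5, ICC 0.05, a realised 15% versus 5% in responders, and a 5% event rate in CAPTURE non-responders. The overall CAPTURE rate is 0.653 × 15 + 0.347 × 5 = 11.5%. Significance is lost when control non-responders reach about 7.3%. The control rate is then 0.653 × 5 + 0.347 × 7.3 = 5.8%, the difference is 5.7 points, and 1.96 × √[(0.115 × 0.885 + 0.058 × 0.942)/183.3] is also 5.7 points. At ICC 0.10 and 0.15 the tipping rates are about 6.2% and 5.2%. This is a large-sample illustration without between-imputation variance, and not a forecast.

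**The case against.** The plan is not blind to arm. The multiple imputation includes intervention group, so imputed outcomes can differ by arm. The all-negative analysis keeps each non-responder's observed chart outcome. The planned tables will show whether non-response, and the available follow-up data of patients with incomplete follow-up, differ by arm. Participants are blinded to the intervention (SAP 7.3), which makes strongly opposed extremes less plausible. The SAP does not call the two single imputations bounds; it presents them as different assumptions. The all-negative analysis is also a transparent chart-based result that should not be lost.

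All of this stands, and it narrows the point. It does not remove it. Multiple imputation handles arm-dependent missingness only under missing at random, and descriptive tables do not test the conclusion.

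Four stronger readings are tempting and are not supported:

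- A reader might infer that common-value imputation can only shrink the difference. For the all-positive rule that holds at equal non-response; at unequal rates the rule can enlarge, reverse or create a difference. The all-negative rule can enlarge it too.
- A reader might infer that the plan ignores arm-dependent non-response. Unequal rates do move the all-positive result, though in an uncontrolled way. What goes untested is arm-dependent outcomes among non-responders.
- A reader might infer that the two rules give the same answer. The match at 6.5 points needs zero chart capture, whereas these imputations are planned only for endpoints collected from both sources.
- A reader might take 35% as the final missing rate. It is an interim count, and only 20 of the 380 were then listed as lost to follow-up.

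**Conclusion.** The concern holds in a limited form. Both single imputations assign one value to both arms, and nothing planned goes beyond missing at random in an arm-specific way. The all-positive result is uninformative about robustness: for a 10-point responder difference it ranges from -2.5 to +15.5 points when assumed non-response moves between 30%/40% and 40%/30% (CAPTURE/control), and it reads +9.5 with no effect at 40%/30%. The all-negative analysis remains useful.

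These sizes rest on the SAP's 5% control rate, a 10-point difference and assumed arm-specific non-response. The equal-rate figures use the pooled interim 34.7%, and the all-negative range also assumes that non-responders share the responders' event rates. Clustering is ignored except in the tipping-point illustration, and it does not change the direction of these results. The documents do not show that non-response will differ by arm or that the primary result will be wrong. This is a cheap improvement to what the trial can say about robustness, and not a flaw in the primary analysis.

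**What to change.** Keep the all-negative analysis and the multiple imputation as written. Replace or supplement the all-positive analysis in SAP 9.5 and 11.2 with a delta-adjusted multiple imputation, and align Protocol 9.3.2:

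- In survey non-responders whose chart is negative, vary the imputed survey event probability separately in each arm over a grid.
- Report the estimate and p-value across the grid, and the smallest arm-specific departure from the missing-at-random imputation that removes significance.
- Give the two arm-opposed extremes as outer bounds, labelled as such.
- If the all-positive result is kept, report it beside non-response by arm and state that it is not a bound.

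The cost is one SAP paragraph and a few extra runs on data already collected. The outer bounds will be wide, so the tipping point is the result to interpret. If the data have already been unblinded, label the analysis as post hoc.
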